4.3.5 Visit 5 – Day 90 (\pm 7 days)

The patient will return 30 days (+/- 7 days) after Visit 4. During this visit, the following will be performed:

- obtain a urine pregnancy test (for women of childbearing potential)
- review current medications
- review the interval medical history and conduct a physical examination
- assess for adverse events
- obtain clinical labs including: CBC, CPK, Complete Metabolic Panel, lipid panel, and sirolimus or everolimus drug level
- obtain blood for VEGF-D measurement and, if the patient has consented obtain an additional sample to be stored on-site for potential future use
- administer the SGRQ and FPI instruments for dyspnea, fatigue and quality of life
- assess for simvastatin drug compliance
- as necessary, perform simvastatin down-titration and manage drug dispensing
- provide a study calendar to document drug compliance. The patient should bring the completed calendar back at Visit 6.

4.3.6 Visit 6 - Day 120 (\pm 7 days)

The patient will return 30 days (+/- 7 days) after Visit 5. During this visit, the following will be performed:

- obtain a urine pregnancy test (for women of childbearing potential)
- review current medications
- review the interval medical history and conduct a physical examination
- assess for adverse events
- obtain clinical labs including: CBC, CPK, Complete Metabolic Panel, lipid panel, and sirolimus or everolimus drug level
- obtain blood for VEGF-D measurement and, if the patient has consented obtain an additional sample to be stored on-site for potential future use
- obtain a chest x-ray
- perform spirometry with appropriate safety procedures. All spirometry tests during all visits will be performed after supervised administration of bronchodilator in the pulmonary function laboratory.
- administer the SGRQ and FPI instruments for dyspnea, fatigue and quality of life
- assess for simvastatin drug compliance
- advise women of childbearing potential that they should continue to use their method of birth control for at least 30 days after the study ends
- remind patients they will be contacted by phone in approximately 30 days as a follow-up.
- remind the patient to follow up with her regular physician for routine care.

If at visit 6, it is determined there has been clinical benefit, the patient and her regular physician will decide how to proceed after the conclusion of the clinical study.

4.3.7 End of Study Telephone Call – Day 150 (+/- 7 days)

An end of study phone call will be conducted at 30 days (+/- 7 days) after the study visit 6. The purpose of the call is to follow up on any open or unresolved adverse events.

5. Dose Limiting Toxicity Rules, Dose Delays, and Dosing Modifications

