7.2 Criteria for Terminating the Study

Up to ten patients will be enrolled in this study. The maximum duration of patient participation is up to 164 days, including a follow-up phone contact one month after the last study visit. In the event of any death, or Grade III SAE attributable to the study agent, enrollment and treatment will be suspended, pending Data Safety Monitoring Board (DSMB) review.

8. Study Variables and Measuring Methods

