9.3. Adverse Events

The investigator must grade AEs according to the National Cancer Institute Common Terminology Criteria for Adverse Events Version 4.0 (CTCAE v4.0) and provide an opinion regarding the causal relationship of the AE to study drug.

Patients will be carefully monitored for adverse events from the initial dose of study medication through the 30 day post telephone call.

All observed or volunteered adverse events, regardless of treatment group or suspected causal relationship to study drug, will be recorded on the adverse event page(s) of the case report form.

Events involving adverse drug reactions, illnesses with onset during the study, or exacerbations of pre-existing illnesses will be recorded. Exacerbation of pre-existing illness, including the disease under study, is defined as a manifestation (sign or symptom) of the illness that indicates a significant increase in the severity of the illness, as compared to the severity noted at the start of the study.

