However, if a hospitalization for an unknown event occurs, it should be considered as a serious adverse event.

Prolongation of hospitalization is defined as any extension of an inpatient hospitalization beyond the stay anticipated/required in relation to the original reason for the initial admission, as determined by the investigator or treating physician.

Preplanned treatments or surgical procedures should be noted in the baseline documentation for the entire protocol and/or for the individual patient.

Disability is a substantial disruption of a person’s ability to conduct normal life functions.

Any serious adverse event or death must be reported to the IRB immediately, independent of the circumstances or suspected cause, if it occurs or comes to the attention of the investigator at any time during the study, through 30 days after the last administration of study drug. Any serious adverse event occurring beyond 30 days after the last administration of study drug must be promptly reported, if a causal relationship to study drug is suspected. The only exception to these reporting requirements are serious adverse events that occur during a pre-randomization/washout run-in period, during which either placebo alone is administered, or no active study drug or protocol-specified background drug is administered.

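### The last safety contact, the end of adverse event monitoring and the SAE window are timed from different points, so a compliant call can end active follow-up up to 7 days before 30 days post-dose

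*Combined protocol and SAP*

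**What the plan says.** Four sections of the combined protocol and SAP bear on when safety follow-up ends.

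- Section 4.3.7 (End of Study Telephone Call): "An end of study phone call will be conducted at 30 days (+/- 7 days) after the study visit 6". Its stated aim is limited: "The purpose of the call is to follow up on any open or unresolved adverse events". The heading places the call at Day 150, plus or minus 7 days.
- Section 9.3 (Adverse Events): monitoring runs "from the initial dose of study medication through the 30 day post telephone call".
- Section 9.3.1 (Serious Adverse Events): SAEs and deaths go to the IRB if they arise "at any time during the study, through 30 days after the last administration of study drug". A later SAE must still be reported if a link to study drug is suspected.
- Section 7.2 (Criteria for Terminating the Study): the maximum participation is given as 164 days, "including a follow-up phone contact one month after the last study visit". Visit 6 is not named.

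Other sections provide follow-up for patients who stop treatment. Section 6.1 continues follow-up assessments and sets out telephone and letter contact after a missed visit. Section 7.1 calls for an attempt at a final visit and for clinical follow-up of study-related events. Section 10.12 treats the remaining scheduled assessments as essential and adds a clinic safety assessment, without a date, if treatment is permanently withdrawn.

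**The concern.** Safety is the primary outcome, and at most 10 patients will be studied, so each event counts. The plan itself treats 30 days after the last dose as the period in which every SAE is reportable whatever its cause. The last planned contact should then come no earlier than the end of that period. Because the call is timed from a visit, and its window opens 7 days early, it need not.

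Two details add to this. The call's stated purpose covers events already open and does not mention asking about new ones. In Table 1 the adverse event review stops at Day 120 and the call has no column. Section 9.3 promises monitoring up to the call, but no procedure says how an event that begins after Visit 6 would be found.

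Patients who stop early matter most here, since adverse events are themselves a reason for stopping simvastatin (Sections 5.2.3 and 9.2). For a patient who then does not attend Visit 6, Sections 4.3.7 and 7.2 point in different directions.

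**Working it through.** **Inputs.** Day 0 is at most 14 days after screening (4.3.2). Visit 6 is nominally Day 120, plus or minus 7 (4.3.6). The call is 30 days, plus or minus 7, after Visit 6 (4.3.7). The SAE window is 30 days after the last dose (9.3.1). Dosing is in the evening (3.5). Expected attrition is 10% (3.4 and 11.1).

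**Step 1: the plan's own figure.** 14 + 120 + 30 = 164 days, which matches Section 7.2. That total places the call exactly 30 days after a nominal Visit 6 and makes no allowance for windows.

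**Step 2: the call window.** 30 − 7 = 23 and 30 + 7 = 37, so 15 calendar days are permitted, from day 23 to day 37 after Visit 6.

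**Step 3: the shortfall.** Let k be the number of days from the last dose to an attended Visit 6. The earliest permitted call is 23 + k days after the last dose. The shortfall against 30 days is max(0, 30 − (23 + k)) = max(0, 7 − k).

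| k (days) | Call, days after last dose (earliest / nominal / latest) | Largest shortfall | Permitted call days that fall short |
|---|---|---|---|
| 0 | 23 / 30 / 37 | 7 days | 7 of 15 |
| 1 | 24 / 31 / 38 | 6 days | 6 of 15 |
| 6 | 29 / 36 / 43 | 1 day | 1 of 15 |
| 7 | 30 / 37 / 44 | none | 0 of 15 |
| 30 | 53 / 60 / 67 | none | 0 of 15 |

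The plan does not fix the date of the last dose. With evening dosing and a daytime Visit 6, k = 1 is the likely case; k = 0 is the extreme. The gap needs both a last dose within 6 days of Visit 6 and an early call.

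**Step 4: the heading of 4.3.7 against its text.** The heading gives Day 143 to 157. Visit 6 at Day 113 to 127 plus 23 to 37 days gives Day 136 to 164. These also need to agree.

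**Step 5: a patient who stops drug and does not attend Visit 6.**

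- 4.3.7: the call is timed from Visit 6, so no date can be derived for her.
- 7.2: the contact follows the last study visit, so it can be read as one month after whichever visit she last attended.
- 9.3: monitoring ends at the call, so its end depends on which of those two readings applies.
- 9.3.1: the window ends 30 days after her last dose, but no contact is timed from that dose.
- 7.1 and 10.12: a final visit is attempted and a safety assessment is held, neither with a date relative to the last dose.

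**Step 6: how many patients.** Section 11.1 uses the 10% attrition to go from 10 patients to 9 with the full 120 days, so about 10 × 0.10 = 1 patient might not complete. If dropouts are independent, the chance of at least one is 1 − 0.9^10 = 65%. This is a planning figure. It does not show that such a patient would go without any contact.

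**The case against.** The strongest reply is that little is lost in practice. On the nominal date there is no shortfall. The SAE reporting duty in Section 9.3.1 does not depend on the call and continues beyond 30 days where a link to drug is suspected. That stands: what can end early is active contact, not the duty to report. The remaining weakness is that an event after an early call comes to light only if someone volunteers it.

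A reader might infer that patients who never reach Visit 6 have no call at all. The documents do not support that. Section 7.2 can be read as giving them one, and Sections 6.1, 7.1 and 10.12 keep patients who stop treatment in follow-up. A patient who withdraws consent may not be reachable under any rule. What stands is that 4.3.7 and 7.2 differ, and that no contact is tied to the last dose.

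A reader might also infer that 9.3.1 defines a different set of events for the safety tables, for example for a patient who stops early but keeps attending. It does not. It is a rule for reporting to the IRB, and it also covers events at any time during the study. Recording is governed by 9.3, and tabulation by 9.2 and 11.2, which take all adverse events in anyone dosed. Limiting the main tables to 30 days after the last dose would be a preference in a descriptive pilot, not the repair of an error.

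Finally, a reader might want to express the gap as a change in the observed SAE rate. The documents give no basis for the probability of an SAE in those few days, so no such effect can be computed.

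**Conclusion.** The point holds as an inconsistency of anchors with a small, definite consequence. Sections 4.3.7, 7.2, 9.3 and 9.3.1 end follow-up by reference to Visit 6, the last study visit, the call and the last dose respectively. A compliant call can end active adverse event contact up to 7 days before the 30-day post-dose window closes if the last dose is on the day of Visit 6, and up to 6 days before if it is the evening before. There is no gap when the call is on its nominal date or when the last dose was 7 or more days before an attended Visit 6.

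For a patient who stops drug and misses Visit 6, whether and when a call is due depends on which section is followed. The result assumes that the text of 4.3.7, rather than its heading, governs the call, and that monitoring ends at the call as 9.3 states. The size is modest, but it bears on the primary outcome and the remedy is nearly free.

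**What to change.** 1. Reconcile Sections 4.3.7, 7.2, 9.3 and 9.3.1 so that they state the same end of active follow-up, and bring the Day 150 heading of 4.3.7 into line with its text.
2. Keep the call after Visit 6, but set its window so that it falls no earlier than 30 days after the last simvastatin dose, for example day 30 to 37 after Visit 6. With k of 0 or more, the earliest call is then 30 + k days after the last dose, so the shortfall is zero. The call should stay tied to Visit 6 for patients who stop drug early but keep attending; timing their only call from the last dose would take away the contact they now have after Visit 6.
3. For a dosed patient who leaves before Visit 6 and still consents to contact, make the call no earlier than 30 days after her last dose.
4. State in 4.3.7 that the call asks about new as well as open adverse events, and add the call to Table 1.

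The cost is wording, up to 7 days' delay for some calls, and about one call per early leaver. The latest permitted call after Visit 6 does not move. The 164 days in 7.2 is already a nominal total: the present window allows 14 + 120 + 37 = 171 days even with Visit 6 on Day 120. It should be described as approximate or recalculated at the same time.

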5.1 Definition of Dose Limiting Toxicity (DLT)

DLTs will be defined by toxicity occurring during the first 5 weeks of this study. A DLT will be any non-pulmonary AE of Grade 3 or higher that is at least possibly treatment-related with the exception of nausea and vomiting which have not been treated with optimal anti-emetic therapy. Any DLT that causes a patient to miss > 28 consecutive days of simvastatin will result in the patient being taken off treatment.

A DLT is defined as a toxicity considered at least possibly related to simvastatin. In this regard, it is important to consider the possibility that co-administration of simvastatin may increase the toxicity of sirolimus or everolimus. Conversely, sirolimus or everolimus might influence the toxicity profile of simvastatin. Thus, it may be difficult to confidently attribute certain observed toxicities solely to either simvastatin and sirolimus, or simvastatin and everolimus. With this potential complication in mind, an attempt will be made to define dose-limiting toxicities (DLTs), which apply specifically to simvastatin. In this study, DLTs will include any possibly, probably, or definitely simvastatin-related Grade 3 or 4 toxicity. Known toxicities specific to sirolimus and everolimus such as mucositis will not be considered dose limiting unless the treating physician considers the toxicity to be exacerbated by simvastatin. Toxicities that will be attributable to simvastatin include but are not limited to abdominal pain, nausea, diarrhea, headache, and infectious complications.

The target DLT rate is $\leq 33\%$. The maximum tolerated dose (MTD) will be defined as a) the dose producing DLT in 2 out of 6 patients, or b) the dose level below the dose which produced DLT in ≥ 2 out of 3 patients, or in ≥ 3 out of 6 patients. Patients will be evaluable for a DLT if they have finished 5 weeks of combined therapies. Patients who are removed from study due to clinical progression prior to the 5 week period will be replaced. Patients will be evaluable for response if they have completed 90% of their expected dose of simvastatin for the 8 weeks. Patients will be evaluated for toxicity if they received at least one dose of simvastatin.

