Preclinical evidence demonstrates that simvastatin acts as a pro-apoptotic agent in *in vitro* and *in vivo* studies in cells and tumor lesions deficient for *TSC2*, inactivation mutation of which cause LAM and TS (3, 4). HMG-CoA reductase inhibitors (statins) are very safe, highly effective therapies used by millions of people (5, 6). Simvastatin decreases cholesterol, reduces cancer incidence, stabilizes the endothelial cell layer and decreases inflammation. In preclinical studies the combination of rapamycin and simvastatin inhibited xenograft tumor growth and completely blocked the recurrence of xenograft tumors after treatment withdrawal (4). In mouse model of LAM, treatment with rapamycin and simvastatin prevented both growth of *TSC2*-null lesions and lung destruction (3). These findings have fundamental translational significance for combinatorial therapeutic strategies to induce the death of LAM cells, potentially obviating the need for continuous, life-long suppressive therapies. We have designed a Phase II, open label, safety trial to initiate the study of this potentially useful intervention.

We propose to conduct a safety study of simvastatin treatment of patients with LAM-S and LAM-TS. We aim to determine the safety of simvastatin in combination with sirolimus or everolimus over 4 months.

[figure not shown]

Figure 1. Deregulated cell signaling in LAM and its therapeutic targeting.

1. Introduction

This document is a protocol for a human research study. This study is to be conducted according to US and international standards of Good Clinical Practice (FDA Title 21 part 312 and International Conference on Harmonization guidelines), applicable government regulations and Institutional research policies and procedures

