3.5.1 Treatment Regimen

We have chosen an intra-patient dose escalation strategy because there is no previous data from human studies to demonstrate the safety of simvastatin in combination with sirolimus or everolimus, in patients with LAM-S and LAM-TS. Dose escalation strategy will be performed only for patients who tolerate 20 mg daily simvastatin. If patients do not tolerate the 20 mg simvastatin dose, the dose will be down-titrated to 10 mg daily. If 20 mg daily is well tolerated, at visit 4 the dose will be increased to 40 mg daily for months 3 and 4. If 40 mg daily is not well tolerated, the dose will be reduced back to 20 mg daily.

Intermediate dose reductions to 15 or 30 mg/day may be undertaken if the side effect(s) is reasonably mild and tolerable.

[figure not shown]
Patients will remain on their current dose of sirolimus or everolimus without interruption, as clinically indicated.

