4.3.4 Visit 4 – Day 60 (\pm 7 days)

The patient will return 30 days (\pm 7 days) after Visit 3. During this visit, the following will be performed:

- obtain a urine pregnancy test (for women of childbearing potential)
- review current medications
- review the interval medical history and conduct a physical examination
- assess for adverse events
- obtain clinical labs including: CBC, CPK, Complete Metabolic Panel, lipid panel, and sirolimus or everolimus drug level
- obtain blood for VEGF-D measurement and, if the patient has consented obtain an additional sample to be stored on-site for potential future use
- perform spirometry with appropriate safety procedures. All spirometry tests during all visits will be performed after supervised administration of bronchodilator in the pulmonary function laboratory.
- administer the SGRQ and FPI instruments for dyspnea, fatigue and quality of life
- assess for simvastatin drug compliance
- dispense simvastatin 40 mg (if not contraindicated) with instructions regarding dosing and a reminder regarding potential side effects
- provide a study calendar to document drug compliance. The patient should bring the completed calendar back at Visit 5.

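### The only DLT period stated in section 5.1 ends at Day 35, before 40 mg is first dispensed, so a DLT rate or MTD based on it includes no 40 mg exposure

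*Combined protocol and SAP*

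**What the plan says.** Section 5.1 (Definition of Dose Limiting Toxicity) sets the counting period: "DLTs will be defined by toxicity occurring during the first 5 weeks of this study". Two more sentences in that section use the same five weeks. One is the evaluability rule, "Patients will be evaluable for a DLT if they have finished 5 weeks of combined therapies". The other replaces patients who leave for clinical progression before the five weeks are up.

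Section 5.1 also contains text that points elsewhere. One sentence counts Grade 3 or 4 toxicity with at least a possible link to simvastatin and gives no time limit. Another says "Patients will be evaluated for toxicity if they received at least one dose of simvastatin". The section sets a target DLT rate of at most 33% and defines the MTD by counts per dose, for example "the dose producing DLT in 2 out of 6 patients".

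On dosing, section 3.5.1 says "Dose escalation strategy will be performed only for patients who tolerate 20 mg daily simvastatin" and that, for those patients, "at visit 4 the dose will be increased to 40 mg daily for months 3 and 4". Section 4.1 keeps everyone on 20 mg, or less if not tolerated, for the first two months. Section 4.3.4 (Visit 4, Day 60) is where staff "dispense simvastatin 40 mg (if not contraindicated) with instructions regarding dosing".

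On purpose, the Abstract states: "We aim to determine the safety of simvastatin in combination with sirolimus or everolimus over 4 months". Section 11.1 assumes 10% attrition from 10 patients, leaving 9 followed for 120 days, and Table 5 gives DLT precision for those 9.

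**The concern.** The DLT rate is the only safety summary in the plan with a numeric target, and it is the quantity in the only precision table. If its period closes before the dose is raised, it describes about five weeks at 20 mg or less and cannot show whether 40 mg meets the 33% target.

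The higher dose matters here. Section 1.4.1 raises the shared CYP3A4 metabolism of simvastatin and rapamycin and a case of rhabdomyolysis on the combination. Section 1.4.2 links muscle toxicity to high dose and gives lower dose caps with certain co-medications. Section 3.5.1 says that escalation was chosen because no human safety data exist for this combination in these patients, and section 1.3.1 makes the later multi-center trial depend on safety being shown. A low five-week rate could be carried into that decision as if it covered the whole regimen.

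Two related problems sit in the same section. It gives two possible denominators, and its MTD rule needs groups of 3 or 6 patients at each dose, whereas this is a single group escalated within patient.

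**Working it through.** **Plan's own figure.** Table 5 gives the chance of seeing no DLT in 9 patients. With true rate p this is (1 − p)^9:
- p = 0.11: 0.89^9 = 35.0%
- p = 0.22: 0.78^9 = 10.7%
- p = 0.33: 0.67^9 = 2.7%
- p = 0.44 and 0.56: 0.5% and 0.06%

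All five agree with the table. They are valid only for DLTs that the rule is able to count.

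**End of the DLT period.** 5 × 7 = Day 35, from Day 0 (Visit 2, when 20 mg is first dispensed). If the study were taken to start at screening, up to 14 days before Day 0, the period could end as early as Day 35 − 14 = Day 21.

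**Start of 40 mg (Visit 4).** Section 4.3.3 sets Visit 3 at 30 ± 7 days after Visit 2, and section 4.3.4 sets Visit 4 at 30 ± 7 days after Visit 3.

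| Reading of the Visit 4 date | First 40 mg | Gap after Day 35 |
|---|---|---|
| Nominal | Day 60 | 60 − 35 = 25 days |
| Window in the section heading | 60 − 7 = Day 53 | 53 − 35 = 18 days |
| Both visit windows chained | (30 − 7) + (30 − 7) = Day 46 | 46 − 35 = 11 days |

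The overlap with 40 mg is zero days on every reading.

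**Share of exposure.** 35/120 = 29% of planned treatment days: 35 of 60 nominal days at 20 mg and 0 of 60 at 40 mg.

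**Illustration of the period (assumed event).** Suppose that one of 9 patients has a related Grade 3 event, and it occurs at 40 mg. Exact (Clopper-Pearson) 95% intervals are:
- five-week period: 0/9, interval 0% to 1 − 0.025^(1/9) = 33.6%
- 120-day period: 1/9 = 11%, interval 0.3% to 48.2%

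Table 5 prints 3% as the lower limit for 1/9; the exact value is 0.3%.

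**Illustration of the denominator (assumed event).** Section 5.2.3 stops simvastatin at once for myositis. Suppose that one of 10 treated patients stops at week 2 because of a DLT:
- five completed weeks required: 0/9, interval 0% to 33.6%
- one dose required: 1/10 = 10%, interval 0.3% to 44.5%

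**MTD rule.** It needs DLT counts of 2/6, at least 2/3 or at least 3/6 at a dose. With up to 10 patients all starting at 20 mg there are no such cohorts, and within the stated period the 40 mg count cannot exist.

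**The case against.** The strongest objection is that section 5.1 does not clearly exclude 40 mg. Its untimed sentence would count a related Grade 3 or 4 event in month 4, and section 11.1 speaks of 120 days. This stands in part. It would go too far to infer that the sponsor decided to exclude 40 mg events. But five weeks is the only period stated, three sentences rely on it, and no section states another. Two analysts could each follow the protocol and report different rates.

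Second, little depends on the number. The primary outcome in section 2.2.1 does not mention DLTs, section 11.2 plans adverse event tables and does not list a DLT rate, and no decision in the protocol uses the 33% target or the MTD. This stands, and it limits the consequence.

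A reader might infer that patients at 40 mg are unprotected or that their toxicity goes unreported. The documents do not support that. Grade 3 holds and CPK stopping (5.2.3), suspension after a death or an attributable Grade III serious event (7.2), and safety board review, event tables and a summary for each patient (9.2) apply without a five-week limit. With up to 10 patients, events at 40 mg would be visible one by one.

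A reader might also infer that early DLTs will be dropped from the rate. That follows only if the five-week evaluability sentence overrides the one-dose sentence. The replacement rule covers progression, not toxicity, and sections 6.1 and 10.12 continue follow-up after treatment stops. The loss is possible, not established.

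**Conclusion.** The concern holds in a limited form. A DLT rate or MTD determined by the only period that section 5.1 states contains no 40 mg exposure, and the plan conflicts with its own four-month aim and with the 120-day frame of section 11.1. The result assumes the planned dosing schedule and that the five-week sentence governs; the choice of visit-window reading does not change it. Under that reading, DLTs arising at 40 mg go uncounted at any true rate, which is a consequence of the definition and not an estimate of harm. The two illustrations rest on assumed events and show only that the reported figure can change with the reading chosen.

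The defect lies in the DLT rate and the MTD statement, not in patient protection or in the collection of safety data. It should be fixed, because the repair is cheap and the rate is the plan's only quantified safety criterion.

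**What to change.** In section 5.1:
- Count a DLT if its onset falls between the first simvastatin dose and the Day 120 visit. Attribute it to the dose at onset, or to the last dose taken if simvastatin is on hold. Later events, up to the 30-day call, stay in the adverse event tables.
- Put every patient who received at least one dose in the DLT denominator. Delete the five-week evaluability sentence. Delete the five-week replacement sentence too, or state that replaced patients stay in the denominator.
- Report the DLT proportion with an exact 95% interval for (a) the whole regimen, to which the 33% target applies, and (b) patients who took at least one 40 mg dose, as a descriptive figure conditional on having tolerated 20 mg.
- List the last simvastatin day for each patient without a DLT.
- Remove the MTD rule, or state that no MTD will be declared.

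In section 11.1, state the same period and denominator, and recompute Table 5 if the denominator is not 9. With 10 patients, for example, the chance of no DLT at a 33% true rate is 0.67^10 = 1.8%.

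**Cost.** Protocol wording and one table. Adverse events and simvastatin dosing are already reviewed at Visits 3 to 6, so no new data are needed. The reported rate may rise because 40 mg events now count. Patients who leave early without a DLT count as DLT-free, which can lower the rate; the listing of last treatment days makes this visible. The 40 mg interval is wider: if 7 patients reach 40 mg (an assumed number) with no DLT, the upper limit is 1 − 0.025^(1/7) = 41.0%, against 30.8% with 10.

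### Section 5.1 both excludes and counts lung events and under-treated nausea as DLTs, and its evaluability rule can drop patients who had a DLT, so the observed DLT rate is not reproducible

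*Combined protocol and SAP*

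**What the plan says.** Section 5.1 (Definition of Dose Limiting Toxicity) limits DLTs to the first 5 weeks and then gives its first rule: "A DLT will be any non-pulmonary AE of Grade 3 or higher that is at least possibly treatment-related". The rule carries one exemption, worded as follows: "with the exception of nausea and vomiting which have not been treated with optimal anti-emetic therapy".

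The next paragraph turns to attribution. It opens with "A DLT is defined as a toxicity considered at least possibly related to simvastatin" and goes on: "DLTs will include any possibly, probably, or definitely simvastatin-related Grade 3 or 4 toxicity". It then lists examples: "Toxicities that will be attributable to simvastatin include but are not limited to abdominal pain, nausea, diarrhea, headache, and infectious complications". Known sirolimus and everolimus toxicities "such as mucositis will not be considered dose limiting unless the treating physician considers the toxicity to be exacerbated by simvastatin".

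The same section sets a target DLT rate of 33% or less, gives an MTD rule, and states who counts: "Patients will be evaluable for a DLT if they have finished 5 weeks of combined therapies". For toxicity in general, one dose of simvastatin is enough.

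Three other sections bear on this:
- **Section 5.2.3** holds simvastatin after any Grade 3 or higher event with a possible or stronger link to it, until the event resolves.
- **Section 5.2.4** lets the investigator attribute unexpectedly severe lung toxicity to simvastatin as well as to the mTOR inhibitor.
- **Section 11.1, Table 5** gives exact confidence intervals for DLT counts out of 9.

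**The concern.** The first rule has two limits, on lung events and on under-treated nausea or vomiting, that the later sentence lacks. Nothing says which governs. Both kinds of event are foreseen: Section 5.2.4 allows a lung event to be attributed to simvastatin, and Section 5.1 itself names nausea as attributable to it. The attribution wording differs too, since the first rule refers to treatment and the later one to simvastatin.

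The evaluability rule adds a second problem. A patient whose simvastatin is held for a DLT may not finish 5 weeks on both drugs, and would then be left out of the rate that her event should raise.

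Safety is the primary outcome, and the DLT rate is the only safety rate with a numeric target. Two readers of the same case report forms could report different rates. Because the study is open label, the governing sentence could be chosen after the event is known.

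**Working it through.** **1. The two counting rules side by side (Section 5.1).**

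| Event in the first 5 weeks | First rule | Later sentence |
|---|---|---|
| Grade 3 lung event linked to simvastatin | out (non-pulmonary only) | in |
| Grade 3 nausea linked to simvastatin, no optimal anti-emetics | out (exception) | in |
| Grade 3 non-pulmonary event linked only to the mTOR inhibitor and not one of its known toxicities | in, if treatment covers both drugs | out |
| Grade 5 non-pulmonary event linked to simvastatin | in (Grade 3 or higher) | not named (Grade 3 or 4) |

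The first two rows are direct conflicts. The third depends on what treatment means. Section 5.2.2 refers to whichever treatment most likely caused the toxicity and allows single-agent continuation, so there it can mean either drug. The Protocol Summary, however, lists only simvastatin as the agent under Treatment. The fourth row is minor, because Section 7.2 suspends the study for any death.

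**2. The plan's own figures.** Inputs from Section 11.1: up to 10 patients and 10% attrition, so 10 × 0.9 = 9. With P(no DLT) = (1 − p)^9 at p = 0.11, 0.22, 0.33, 0.44 and 0.56, the results are 35.0%, 10.7%, 2.7%, 0.5% and 0.06%. These reproduce Table 5's probability row. The exact (Clopper-Pearson) intervals for 2/9 (2.8% to 60.0%) and 3/9 (7.5% to 70.1%) also agree with the table after rounding. Some of its other printed limits do not, which is a separate matter. All these entries take the count as given, so the DLT definition does not enter them.

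**3. One reclassified patient.** At n = 9 one patient is 1/9 = 11.1 percentage points.
- 3/9 = 33%, exact 95% CI 7.5% to 70.1%.
- 4/9 = 44%, exact 95% CI 13.7% to 78.8%.

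I treat 3/9 as meeting the target because the MTD rule accepts the same proportion: "The maximum tolerated dose (MTD) will be defined as a) the dose producing DLT in 2 out of 6 patients", and 2/6 = 33.3%.

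**4. Chance of being on that boundary.** P(X = 4) = C(9,4) p^4 (1 − p)^5 at Table 5's rates:

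| True rate | 1/9 | 2/9 | 3/9 | 4/9 | 5/9 |
|---|---|---|---|---|---|
| P(exactly 4 of 9) | 1.1% | 8.7% | 20.5% | 26.0% | 20.8% |

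If 33.3% is instead read as above 33%, the boundary lies between 2/9 and 3/9, and P(X = 3) is 5.7%, 20.4%, 27.3%, 21.7% and 11.1%. For a single reclassification to matter, one of those patients must also qualify only through a disputed event. These figures are therefore upper bounds on a one-patient flip.

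**5. The denominator.** Removing one patient with a DLT changes k/n to (k − 1)/(n − 1). The change is −(n − k)/[n(n − 1)], which is negative whenever k < n, so the bias is always downward. Illustration: 4 DLTs in 10 dosed patients is 40% (exact 95% CI 12.2% to 73.8%). If one of the four did not finish 5 weeks, the rate is 3/9 = 33.3%. The change is −6/90 = −6.7 points.

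**The case against.** It can fairly be said that the section is less contradictory than it looks, and that little depends on it.

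- **Three definitions?** A reader might infer that "A DLT is defined as a toxicity considered at least possibly related to simvastatin" is a third, grade-free definition that lets in Grade 1 and 2 events. The documents do not support that: the sentence opens a paragraph on attribution and reads most naturally as an attribution condition. The grade difference is then Grade 5 alone. This part of the objection stands.
- **The later sentence may only refine attribution within the first rule's limits, or its list may not be exhaustive.** The first reading is available, but nothing in the text settles it. The second does not help: if the later sentence adds to the first rule, its word *any* removes both limits for simvastatin-related Grade 3 or 4 events.
- **Table 5.** A reader might infer that the table is invalidated. It is not, because its entries are conditional on a given count.
- **The MTD.** A reader might infer that 2/6 against 3/6 would change the selected dose. The trial has no cohorts of 3 or 6, and the 5-week window (35 days) closes before the day-60 step to 40 mg, so the rule has little bearing here.
- **Patient safety.** No action is tied to the 33% target. Section 7.2 suspends the study for a death or an attributable Grade III SAE, and Section 9.2 stops simvastatin for a serious AE pending DSMB review. Neither uses the DLT label, and all AEs are recorded and tabulated. This stands.
- **The denominator.** The DLT and toxicity populations serve different purposes, a hold can end in reinstatement, and Section 7.1 keeps data acquired before termination in the primary analysis. So loss of a patient is possible, not certain. But Section 7.1 is a general statement and does not clearly override the specific evaluability rule.
- **Section 5.2.4.** Its sentence attributing known mTOR-inhibitor toxicities only to those drugs might seem to contradict the exacerbation clause in Section 5.1. It sits in a dose-modification section and does not say whether it governs DLT counting, so a contradiction is not shown.

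**Conclusion.** The point holds for the observed DLT rate and no further. Section 5.1 classifies two foreseeable event types in opposite ways, leaves attribution open, and has an evaluability rule that, read literally, can remove a patient with a DLT and bias the rate low. With 9 evaluable patients one such case moves the rate by 11.1 points and can separate a result at the target from one above it.

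This rests on two assumptions: that 9 patients are evaluable, as in Section 11.1, and that at least one patient's only qualifying event is of a disputed kind. The documents do not say how likely the second is. At a true rate of 1/9 the chance of sitting on the decisive count is about 1%, so in a well-tolerated study the ambiguity would seldom matter. No passage tests a confidence interval against 33%, and none is assumed here. The loss is in the interpretability of one rate, not in the safety record. It is worth correcting but does not threaten the trial.

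**What to change.** **Definition.** The sponsor should reconcile the sentences of Section 5.1, together with the attribution wording in Sections 5.2.2 and 5.2.4, into one counting definition. It should settle lung events, the anti-emetic exception, which drug or drugs attribution refers to, and Grade 5. Which clinical rule to adopt is the sponsor's choice, and none is proposed here.

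**Denominator and reporting.** Report the DLT rate with an exact 95% CI on a denominator that keeps every patient who has a DLT or stops early for toxicity. All dosed patients would do, and Section 5.1 already uses that set for toxicity. Footnote how many left the 5-week window early without an event.

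**Optional companion row.** Beside it, show the number of patients with any Grade 3 or higher AE in the window, regardless of attribution. That count does not depend on which sentence governs.

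**Cost.** A few sentences of protocol wording and one or two descriptive table rows, built from the AE severity, duration and causality records that Sections 9.2 and 9.3 already require. The companion row will look higher than the DLT rate because it includes background mTOR-inhibitor and LAM events; showing the two together makes the difference visible. Neither row triggers a treatment decision.
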